### **3.2. Discussion of Design**

This study is designed to evaluate the cumulative incidence of newly diagnosed HCC in patients with advanced fibrosis and compensated cirrhosis during 240 weeks of TDF treatment. It will also provide long-term efficacy and safety data (up to 240 weeks) of TDF 300 mg QD.

It is accepted that long-term antiviral therapy benefits cirrhotic patients as will be investigated in this study with TDF. As HCC develops at an annual incidence of approximately 3–6 % in patients with cirrhosis it will take some time to observe an effect of TDF on prevention of HCC, and on histological improvement.

CHB patients with advanced fibrosis and cirrhosis have severe liver disease and reducing viral replication and achieving HBV DNA undetectability is particularly important in this group. In this study subjects with poor response or virological breakthrough after Week 48 (See Section 3.1) may receive rescue treatment, with add-on treatment of additional NAs. Before rescue treatment, serum sample should be collected for resistance testing.

## 4. SUBJECT SELECTION AND WITHDRAWAL CRITERIA

### 4.1. Number of Subjects

186 Chinese CHB subjects with advanced fibrosis & compensated cirrhosis will be administered to TDF 300 mg QD.

Screened	260
Enrolled	186
Completed/evaluable	158

### 4.2. Inclusion Criteria

Specific information regarding warnings, precautions, contraindications, adverse events, and other pertinent information on the GSK investigational product or other study treatment that may impact subject eligibility is provided in the IB/IB supplement(s) and product label.

Deviations from inclusion criteria are not allowed because they can potentially jeopardise the scientific integrity of the study, regulatory acceptability or subject safety. Therefore, adherence to the criteria as specified in the protocol is essential.

Subjects eligible for enrolment in the study must meet all of the following criteria:

1. Age 18-60 years(inclusive);
2. Presence of HBsAg in serum at screening and for at least 6 months before screening assessment;
3. Serum HBV DNA  $\geq$  2000 IU/mL if HBeAg positive at screening (with or without ALT elevation); or serum HBV DNA  $\geq$  200IU/mL if HBeAg negative at screening (with or without ALT elevation);
4. Pathologically or clinically diagnosed as advanced fibrosis or compensated cirrhosis defined as one of following(a or b) :
  - a. Liver biopsy showing advanced fibrosis or cirrhosis (Ishak score  $\geq$ 4 or Fibrosis stage  $\geq$ S3 by Scheuer Score, or within the previous 6 months before baseline and provided that no treatment likely to improve liver histology has been taken since). The slides must be available for review by an independent histopathologist.
  - b. Clinical diagnosis: liver stiffness measure (LSM)  $>$ 12.4 kpa (ALT  $>$  ULN) or LSM  $>$ 9.0 kpa (ALT  $\leq$ ULN), (See section 6.2.7) plus one of the following:
    - i. Endoscopy-proven gastroesophageal or gastric varices, non-cirrhotic portal hypertension excluded;
    - ii. Abdominal ultrasound or CT found changes indicating cirrhosis, irregular liver surface or nodularity, with/without splenomegaly(depth of spleen  $>$ 4.0cm or spleen length  $>$ 13cm);
    - iii. Blood platelets  $<$ 100  $\times 10^9/L$  (and other causes of thrombocytopenia excluded);

5. Ability to give written informed consent;
6. A female is eligible to enter and participate in this study if she is of:
  - a. non-childbearing potential (i.e., physiologically incapable of becoming pregnant, including any female who is post-menopausal), or
  - b. Child-bearing potential, has a negative urine pregnancy test at screening, and agrees to one of the following methods for avoidance of pregnancy during the period of the study and until 30 days after last dose of study medication:
    - i. Oral contraceptive, either combined or progestogen alone.
    - ii. Injectable progestogen.
    - iii. Implants of levonorgestrel.
    - iv. Oestrogenic vaginal ring.
    - v. Percutaneous contraceptive patches.
    - vi. Intrauterine device (IUD) or intrauterine system (IUS) showing that the expected failure rate is less than 1% per year as stated in the IUD or IUS product label.
    - vii. Has a male partner who is sterilised.
    - viii. Double barrier method: condom and an occlusive cap (diaphragm or cervical/vault caps) with a vaginal spermicidal agent (foam/gel/film/cream/suppository).
7. Agreement not to participate in any other investigational trials or to undertake other HBV systemic antiviral or IFN regimens during participation in this study.

  12. Use of immunosuppressive therapy, immunomodulatory therapy (including IFN or thymosin α), systemic cytotoxic agents, chronic antiviral agents including Chinese herbal medicines known to have activity against HBV (e.g., LAM, adefovir, ETV LdT or hepatitis B immunoglobulin (HBIG)) within the previous 6 months prior to screening into this study;
  13. Have ever received TDF or any medicinal products containing the above mentioned antiviral agents or any investigative anti-HBV treatments (e.g., emtricitabine (FTC), (2*R*, 4*R*)-4-(2, 6-Diaminopurin-9-yl)-1, 3-dioxolan-2-yl]methanol (DAPD) and 1-(2-fluoro-5-methyl-beta, Larabinofuranosyl) uracil (L-FMAU));
  14. History of hypersensitivity to nucleoside and/or nucleotide analogues and/or any component of study medication;
  15. Therapy with nephrotoxic drugs (e.g., aminoglycosides, amphotericin B, vancomycin, cidofovir, foscarnet, cis-platinum, pentamidine etc.) or competitors of renal excretion (e.g., probenecid) within 2 months prior to study screening or the expectation that subject will receive any of these during the course of the study;
  16. Inability to comply with study requirements as determined by the study Investigator.

#### **4.4. Withdrawal Criteria**

Should a subject fail to attend the clinic for a required study visit, the site should attempt to contact the subject and re-schedule the missed visit as soon as possible. The site should also counsel the subject on the importance of maintaining the assigned visit schedule and ascertain whether or not the subject wishes to and/or should continue in the study based on previous non-compliance. In cases where the subject does not return for the rescheduled visit or cannot be reached to reschedule the missed visit, the site should make every effort to regain contact with the subject (3 telephone calls and if necessary a certified letter to the subject's last known mailing address) so that they can appropriately be withdrawn from the study. These contact attempts should be documented in the subject's medical record. Should the subject continue to be unreachable, then and only

then will he/she be considered to have withdrawn from the study with a primary reason of “Lost to Follow-up”. For all other subjects withdrawing from the study, an alternative reason for discontinuation should be recorded in the eCRF.

Subjects who temporarily interrupted treatment for <28 consecutive days were allowed to continue in the study. Subjects with treatment interruptions of  $\geq 28$  consecutive days were required to withdraw from the study.

A subject may voluntarily discontinue participation in this study at any time. The investigator also have the right to withdraw patients from treatment or the study in the event of intercurrent illness, adverse events, protocol violations, administrative reasons or other reasons at any time. Any female subject who becomes pregnant while participating should withdraw from the study. The reason for withdrawal from the study must be recorded in the case report form (CRF).

Subjects will also be withdrawn from the study if they reached primary end-point. These subjects will be eligible for study drugs and originally scheduled follow-up.

Subjects who have received at least one dose of study drug and permanently discontinued the study drug should be followed up by the investigator as described in Table 1.

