	serum concentrations of tenofovir and/or increase the concentrations of other renally eliminated drugs. Some examples include, but are not limited to cidofovir, acyclovir, valacyclovir, ganciclovir, valganciclovir, aminoglycosides (e.g., gentamicin), and high-dose or multiple NSAIDs	with concurrent or recent use of a nephrotoxic agent according to the protocol (See section 5.6.2)
Post-treatment hepatic flares	Discontinuation of anti-HBV therapy, including VIREAD, may be associated with severe acute exacerbations of hepatitis and must only take place under careful supervision.	
 
• Patients who withdraw from the investigational product during treatment period will be followed as per the original schedule.
 
• No post-study medication is provided; the investigator is responsible for ensuring that consideration has been given to the post-study care of the patient's medical condition.
 

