## **3. INVESTIGATIONAL PLAN**

### **3.1. Study Design**

This is a prospective, multi-centre, open-label, cohort study to investigate efficacy and safety of Tenofovir Disoproxil Fumarate (TDF) treatment in Chinese CHB subjects with advanced fibrosis and compensated cirrhosis. The study will enrol 186 subjects with a diagnosis of CHB and advanced fibrosis or compensated cirrhosis.

Screen phase ( $\leq 4$  weeks): Written informed consent must be obtained from each subject prior to participation in the study. Subjects considered eligible to enroll in the study will be assessed at a screening visit as described in Table 1 to decide if they meet the study criteria (see that in 4.2 and 4.3). Between Screen visit and baseline visit, subjects will not receive investigational product.

Treatment phase: 186 subjects will be administered TDF 300 mg QD and undergo regular safety and efficacy assessments every 12 weeks for a total of up to 240 weeks (see Table 1). Subjects will be questioned about adverse events, concurrent medications, and study drug accountability; blood will be taken for hematology and biochemistry profiles; serum samples will be tested for HBV markers, and the prothrombin time will be measured. Serum samples will be collected at Week 12, 24,36, 48, 60, 72, 84, and 96 and every 24 weeks thereafter and analyzed for HBV DNA levels at a central laboratory. Abdominal ultrasound, the prothrombin time and serum alpha-fetoprotein test will be performed every visits. If abdominal ultrasound reports a liver mass or nodule, CT or MRI will be performed. At baseline and W216, 100 of subjects will take liver biopsy to

evaluate liver histological changes pre and post TDF treatment. All subjects will be followed through to Week 240.

Rescue treatment could be optionally initiated in subjects with unsatisfied response to TDF, at the discretion of the investigator if

- subjects have confirmed virological breakthrough as defined by  $\geq$  one log increase in HBV DNA from nadir determined by two sequential HBV DNA measurements at least 1 month apart, or
- subjects have HBV DNA  $\geq$ 200IU/ml at week 48 and afterwards have  $\leq$  one log decrease in HBV DNA at two consecutive visits, confirmed by a third visit at least one month apart.

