- 3 In the event of early study drug discontinuation, the evaluation should be performed in 12 weeks after discontinuation of study treatment.
- 4 Medical history will include any acute and chronic medical conditions including prior surgery, information related to hepatitis B history, any current and prior HBV medications, and previous HBV-related procedures.
- 5 Update any new medical conditions and/or concomitant medications that have occurred since study screening.
- 6 Concomitant medications including traditional Chinese medicines and/or herbal remedies.
- 7 At screening, a complete physical examination will be performed. For all following indicated visits, a brief physical examination will be performed.
- 8 Including blood pressure, pulse, respiratory rate and temperature.
- 9 Urine pregnancy test will be performed at screening, baseline and every 3 months after dosing.
- 10 HBV DNA will be tested using Roche COBAS Taqman HBV test(LLD 20 IU/mL).
- 11 Each study visit: All study medication to be collected and reconciled.

- 12 Liver biopsy will be done in 100 subjects in sites at baseline and week 216. Liver biopsy can be done at screening (Visit 1) or at baseline (Visit 2), at the discretion of investigator. Liver biopsy slides within 6 months prior to baseline can be accepted as baseline evaluation.
- 13 Tests will be performed at central lab
- 14 Demographic data includes birth date, gender and race
- 15 B ultrasound examination include liver, pancreas, spleen, gall bladder and kidney
- 16 Urinalysis: urine glucose, ketones, specific gravity, blood, pH and protein
- 17 Serum will be collected as scheduled for potential resistance surveillance. Genotypic analysis will be performed under the condition defined in protocol (see section 6.2.8)
- 18 Genotyping will be performed at central lab at screen

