7. STATISTICAL ANALYSIS

7.1 Subject screening, disposition and protocol deviations

The screening failure subjects and the reasons for screening failure will be summarized by the numbers and percentages. The percentages are based on the number of screening failure subjects.

The disposition of subjects will be summarized, including the numbers and percentages of subjects for the following categories: all enrolled subjects, subjects completed the study, subjects early discontinued from the study, subjects in the modified intent to treat population, subjects in the per-protocol population, and subjects in the safety analysis population. All percentages are based on the number of all enrolled subjects.

The primary reason for subject premature discontinuation from study will also be summarized. The reasons for discontinuation will include voluntarily discontinue participation, lost to follow-up, lack of efficacy, subjects with treatment interruptions of ≥ 28 consecutive days, adverse event, intercurrent illness, protocol violations, pregnancy, and other reason. A listing will be provided.

Major protocol deviations will be summarized and listed for mITT population. Subject counts and percentages will be displayed by the following deviation categories:

- Eligibility criteria not met
- Excluded medication, vaccine or device
- Assessment or time point completion
- Wrong study treatment/administration/dose

Major protocol deviations which results in the exclusion of the subject from PP population will be discussed, determined, and documented by study team before final database lock. A listing of subject disposition in analysis data sets will be provide.

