7.4.1 Analysis of primary variables

The primary efficacy endpoints for this study are the 240-Week cumulative incidence of newly diagnosed HCC and 240-Week cumulative incidence of disease progression. The newly diagnosed HCC is defined as HCC cases from Week 24 to Week 240. The analysis will be performed in mITT and PP population.

- Nominal cumulative incidence of newly diagnosed HCC at week 240 is defined as the percentage of patient who are newly diagnosed as HCC from Week 24 visit to Week 240 visit in overall patients. Nominal cumulative incidence of HCC will be summarized by frequency, percentage and its 95% two-sided Wald CI. When the value of the newly diagnosed HCC at week 240 is missing due to the epidemic of COVID-19, the missing value may be imputed with the value at the safety follow-up visit. Different missing imputation scenarios will be assessed for the primary analysis and sensitivity analyses, details are provided in below table in which “Y” means the missing value will be imputed with the value at the safety follow-up visit.

Difference between planned Week 240 visit and actual safety follow up visit	Medication taken after previous visit	Primary Endpoints	Sensitivity Analysis 1	Sensitivity Analysis2
<=28 days	Any	Y	Y	Y
>28 days	GSK	Y	N	Y
	Domestic	Y	N	N
	Both GSK & domestic	Y	N	N
Lost to follow up	NA	N	N	N

- Nominal cumulative incidence of disease progression at week 240 is defined as the percentage of patient who have disease progression before Week 240 visit in overall

patients. Nominal cumulative incidence of disease progression will be summarized by frequency, percentage and its 95% two-sided Wald CI. When the value of the disease progression at week 240 is missing due to the epidemic of COVID-19, the missing value will be imputed with the value at the safety follow-up visit. No sensitive analysis is planned.

- Cumulative incidence of newly diagnosed HCC/disease progression at week 240 and its 95% CI will be estimated from the Kaplan–Meier analysis. Time to newly diagnosed HCC/disease progression is defined as the interval between the date of first treatment dose and the analysis date. The rules of analysis date are described in the following table:

Patient's Condition	Status	Analysis date
Diagnosed HCC/disease progression on visit	Event	Date of diagnosis
Reported SAE related with HCC/disease progression between visits	Event	Date of diagnosis
Complete study without HCC/disease progression	Censor	Date of study complete

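### Two conflicting rules govern follow-up after TDF is stopped, and the nominal HCC and progression rates depend on which one is applied

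*Protocol*

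**What the plan says.** **Leaving the study.** Protocol section 4.4 states that subjects whose treatment is interrupted for 28 or more "consecutive days were required to withdraw from the study". SAP section 7.1 carries this forward: its reasons for premature discontinuation from the study include interruptions of at least 28 "consecutive days, adverse event, intercurrent illness, protocol violations, pregnancy, and other reason". Section 4.4 also says that subjects who took at least one dose and "permanently discontinued the study drug should be followed up by the investigator as described in Table 1". Table 1 has a single withdrawal column, and its footnote 3 reads "In the event of early study drug discontinuation, the evaluation should be performed in 12 weeks after discontinuation of study treatment".

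**Staying on schedule.** The mitigation column of Protocol section 1.3.1 says "Patients who withdraw from the investigational product during treatment period will be followed as per the original schedule". Section 3.1 says "All subjects will be followed through to Week 240", and the Protocol Summary says the same in substance.

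**Analysis.** SAP section 7.4.1 defines the nominal HCC rate as the "percentage of patient who are newly diagnosed as HCC from Week 24 visit to Week 240 visit in overall patients". Nominal progression likewise uses all patients as denominator. The Kaplan-Meier table in that section censors early withdrawals at the last visit with adequate diagnostic data. Neither document says whether events or time after stopping TDF count.

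**The concern.** Anyone who stops TDF permanently passes 28 days off drug, so both sets of statements reach the same subject. One site could end scheduled assessment after an exit visit while another continues 12-weekly surveillance to Week 240, and both could cite the protocol.

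Both primary endpoints are 240-week incidences in the mITT population. If later outcomes are not collected, the nominal rate treats the unobserved time as event-free and can only fall. The loss may also be related to risk. Section 6.3.2 ties discontinuation to confirmed creatinine elevation, while renal insufficiency is a component of progression. Section 6.3.1.1 warns that stopping could lead to decompensation. The same section also directs subjects with bridging fibrosis or cirrhosis to commercial HBV therapy after stopping, which could limit any excess risk.

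The two planned sensitivity analyses address only Week 240 HCC values missing because of COVID-19. None is planned for progression.

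**Working it through.** **The plan's own figures.** With p = 5%, a half-width of 3.4 points and z = 1.96:

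- N = 0.05 × 0.95 × (1.96/0.034)² = 157.9, i.e. 158.
- With 15% drop-out, 158/0.85 = 185.9, i.e. 186.

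Both reproduce, and neither is in dispute. At N = 186 the half-width is 1.96 × √(0.05 × 0.95/186) = 3.1 points.

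**Inputs for the effect of the rules**

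- True HCC incidence over Weeks 24 to 240: 5% (Protocol section 8.2.1).
- Share s who stop TDF: not in the documents. I use 15%, the plan's total drop-out (about 28 of 186), as an upper-end value, and 5% (about 9) as a lower one.
- Stopping time U uniform over Weeks 0 to 240, constant hazard, off-drug hazard ratio h of 1, 2 or 4: all assumptions.

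**Formulas.** Let λ be the weekly on-drug hazard, on = max(U, 24) − 24 and off = 216 − on. E is the average over U.

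- Truth: (1 − s)(1 − e^(−216λ)) + s·E[1 − e^(−λ·on − hλ·off)] = 5%, solved for λ.
- Nominal rate if stoppers are withdrawn at stopping: (1 − s)(1 − e^(−216λ)) + s·E[1 − e^(−λ·on)].
- Kaplan-Meier, censored at stopping: 1 − e^(−216λ).

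**Worked cases, s = 15%**

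- h = 1: 0.85 × 5.00 + 0.15 × 2.27 = 4.59%.
- h = 2: 0.85 × 4.63 + 0.15 × 2.10 = 4.25%.
- h = 4: 0.85 × 4.06 + 0.15 × 1.84 = 3.73%.

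| Stop TDF | Off-drug hazard ratio | Nominal, withdrawn at stopping | Nominal, with 12-week exit visit | Kaplan-Meier |
|---|---|---|---|---|
| 15% | 1 | 4.59% | 4.63% | 5.00% |
| 15% | 2 | 4.25% | 4.32% | 4.63% |
| 15% | 4 | 3.73% | 3.85% | 4.06% |
| 5% | 1 | 4.86% | 4.88% | 5.00% |
| 5% | 2 | 4.74% | 4.76% | 4.87% |
| 5% | 4 | 4.52% | 4.56% | 4.65% |

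Full follow-up to Week 240 gives 5.00% in every row. Adding the exit visit changes the nominal rate by at most 0.12 points, so withdrawal and exit visit behave as one rule.

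**Unobserved time.** The average off-drug time inside the window is 118.8 weeks (2.28 years). For 28 stoppers that is about 64 person-years.

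**Progression.** The documents give no expected rate. Fixing the on-drug rate at an assumed 10% or 20%, with 28 stoppers and hazard ratios of 1 to 3, the nominal rate falls short of full follow-up by 0.7 to 2.1 or 1.5 to 3.8 points.

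**The case against.** A reader might infer three incompatible rules: withdrawal, one visit at 12 weeks, and the original schedule. The text does not support that. Section 4.4 itself sends permanent discontinuers to Table 1, whose withdrawal column reads naturally as the exit visit, and the two give nearly equal rates. There are two rules in conflict.

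A reader might also infer that withdrawn subjects contribute no outcome data. That is wrong. The mITT population keeps everyone with one dose, data up to stopping are used, and the exit visit includes ultrasound, AFP, chemistry and prothrombin time. SAP section 7.4.1 also counts events reported as SAEs between visits. What is lost is scheduled assessment after that.

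Three further objections carry weight:

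- Kaplan-Meier, which Protocol section 8.3.5.1 names for the primary outcome, is unbiased when stopping is unrelated to risk and off-drug risk is unchanged. It then loses only precision.
- The 15% includes withdrawal of consent and loss to follow-up, which no rewording recovers.
- The objective concerns incidence during 240 weeks of TDF treatment, so censoring soon after stopping is defensible for an on-treatment question.

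The last objection does not rescue the nominal rate, which keeps stoppers in the denominator for the whole 240 weeks. Nor does it settle the text, because the documents never say which question is meant.

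**Conclusion.** The contradiction stands: Protocol section 4.4, Table 1 footnote 3 and SAP section 7.1 on one side, Protocol section 1.3.1, section 3.1 and the Protocol Summary on the other. Applying the withdrawal rule lowers the nominal HCC rate by 0.4 to 1.3 points from 5% if 15% stop, and by 0.1 to 0.5 points if 5% stop, over hazard ratios of 1 to 4. All these shifts lie inside the planned 3.4-point margin. They run in one direction, however, and the confidence interval does not reflect them.

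The nominal rate falls even when stopping is unrelated to risk. Kaplan-Meier is biased only if off-drug risk differs or stopping is related to risk. The stopping rate, the off-drug hazard ratios and the progression rates are assumptions, since the documents give none of them. The material does not show that informative loss will occur, only that the plan leaves room for it and has no analysis that would reveal it.

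**What to change.** 1. Reconcile the Protocol Summary, Protocol sections 1.3.1, 3.1 and 4.4, Table 1 footnote 3 and SAP section 7.1 into one follow-up rule that separates stopping study drug from leaving the study. The stopping and treatment rules themselves are for the sponsor to decide.
2. State in SAP section 7.4.1 whether events and time after stopping TDF count in each primary endpoint, for both the nominal and the Kaplan-Meier estimates.
3. Report the number of subjects who stopped TDF and their unobserved time to Week 240. Add a sensitivity analysis for HCC and for progression over a range of off-drug risks.

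The cost is protocol wording, possibly some visits already in the schedule for subjects off drug, and a little extra analysis. The SAP is dated February 2021, so follow-up may already be over. Items 2 and 3 can still be done from the data collected.

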Confirmation of HBV DNA test will require an additional visit to collect serum sample. To receive rescue treatment subjects must have investigational product (IP) compliance  $>$  80% in the last regular visits period (usually 12 weeks). Add-on combination with a nucleoside agent (LAM, ETV or LdT) is acceptable rescue treatment in this study, as to investigator's decision. Before rescue treatment, serum sample should be collected for resistance testing.

Subjects who reach primary endpoint (i.e. develop liver complications or HCC) may withdraw from study. Investigator and subjects can decide whether to continue study drug. Subjects who continue to take study drug will be followed as per the original schedule until Week 240. During the follow-up period, AEs, concomitant medication, vital signs, hepatitis B virus DNA, haematology, chemistry and prothrombin will be evaluated. Serum/plasma storage also will be conducted.

Supplementary study conduct information not mandated to be present in this protocol is provided in the accompanying Study Procedures Manual (SPM). The SPM will provide the site personnel with administrative and detailed technical information that does not affect subject safety.

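### The plan gives conflicting rules for follow-up after a non-HCC progression event, so HCC surveillance to Week 240 is not secured for subjects still at risk for the HCC co-primary endpoint

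*Protocol*

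**What the plan says.** There are two primary endpoints (SAP 7.4.1): 240-week cumulative incidence of newly diagnosed HCC, and of disease progression. Progression includes events that are not HCC: a Child-Pugh rise of 2 or more points, peritonitis, confirmed creatinine clearance of 50 mL/min or less, and variceal bleeding.

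On subjects who reach a primary endpoint:
- Protocol 4.4: "Subjects will also be withdrawn from the study if they reached primary end-point". The next sentence reads "These subjects will be eligible for study drugs and originally scheduled follow-up".
- Protocol 3.1, with the same rule in the protocol summary and SAP 3.1: "Subjects who reach primary endpoint (i.e. develop liver complications or HCC) may withdraw from study". It adds "Subjects who continue to take study drug will be followed as per the original schedule until Week 240" and then "During the follow-up period, AEs, concomitant medication, vital signs, hepatitis B virus DNA, haematology, chemistry and prothrombin will be evaluated".
- Protocol 3.1 also says "All subjects will be followed through to Week 240"; the summary and SAP 3.1 agree.

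On subjects who stop or interrupt drug:
- Protocol 1.3.1 keeps subjects who come off the product on the original schedule.
- Protocol 4.4 says those who have "permanently discontinued the study drug should be followed up by the investigator as described in Table 1". Footnote 3 of that table describes an evaluation in the 12 weeks after stopping.
- Protocol 4.4 also says that subjects with an interruption of 28 or more "consecutive days were required to withdraw from the study".

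On analysis: the nominal HCC rate in SAP 7.4.1 divides by all patients, and Protocol 8.3.5 takes the last available visit for non-completers. The Kaplan-Meier analysis censors early withdrawals at the last visit with adequate diagnostic data.

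**The concern.** A subject with, say, a confirmed renal event has reached one primary endpoint but not the other. The plan tells the site that this subject is withdrawn, may withdraw, remains eligible for scheduled visits, and is followed to Week 240. These cannot all be applied as written, so sites may handle the same event differently.

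If such a subject leaves, a later HCC is not seen. The subject stays in the nominal denominator as HCC-free, so any error in that rate is downward, which flatters the treatment. In the Kaplan-Meier analysis the subject is censored. That does no harm if HCC risk is unchanged by progression, but biases the estimate down if risk is higher afterwards. The confidence interval does not allow for this bias. Protocol 8.1 states that no hypothesis is tested, so what is at stake is the accuracy of the estimate, not a test decision.

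**Working it through.** **1. The plan's own figures.** Protocol 8.2.1 and SAP 3.2.1 assume p = 0.05 and a 95% half-width e = 0.034.
- N = p(1 − p)(z/e)² = 0.05 × 0.95 × (1.96/0.034)² = 157.8, so 158.
- Half-width at 158 = 1.96 × √(0.05 × 0.95/158) = 0.0340.
- With 15% dropout, 158/0.85 = 185.9, so 186.

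All agree with the plan, and nothing below alters them.

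**2. Follow-up for HCC after a non-HCC event, by situation.**

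| Situation | Text that keeps surveillance | Text that weakens it |
|---|---|---|
| Continues drug | 3.1: original schedule to Week 240 | 4.4: will be withdrawn; 3.1: may withdraw |
| Stops drug | 1.3.1: original schedule | Table 1 footnote 3: evaluation within 12 weeks of stopping |
| Interrupts drug for 28 days or more | 1.3.1, if the subject counts as off the product | 4.4: must withdraw from the study |
| Any | 3.1: all followed to Week 240; 4.4: eligible for scheduled follow-up | 4.4: will be withdrawn; eligibility is not a requirement |

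The first row is nearly secure. The second and third are not.

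**3. Unit of loss.** Expected HCC cases: 0.05 × 186 = 9.3. One missed case lowers the nominal rate by 1/186 = 0.54 points.

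**4. Illustration of size.** The documents give no progression rate, no HCC hazard ratio after progression and no fraction lost, so all three are assumptions. The model has three states (event-free, progressed without HCC, HCC) and constant hazards over 240 weeks, scaled to 1. It ignores the Week 24 start for newly diagnosed HCC, and all other dropout.
- Progression hazard g = −ln(1 − q), where q is assumed 240-week progression.
- HCC hazard is h before progression and HR × h after it, with h solved so that true HCC is 5%.
- A fraction f of progressors leaves at progression.
- Nominal = (HCC before progression) + (1 − f) × (HCC after progression).
- Kaplan-Meier = 1 − exp(−integral of the average HCC hazard among those still followed).

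Worked case, q = 10% and HR = 2: g = 0.105 and h = 0.0489. HCC before progression is 4.53% and after it 0.47%, total 5.00%. With f = 25%, nominal = 4.53 + 0.75 × 0.47 = 4.88%, and cases missed = 186 × 0.25 × 0.0047 = 0.22.

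Results at q = 10%, as nominal / Kaplan-Meier (%):

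| Lost | HR 1 | HR 2 | HR 4 |
|---|---|---|---|
| 0% | 5.00 / 5.00 | 5.00 / 5.00 | 5.00 / 5.00 |
| 10% | 4.97 / 5.00 | 4.95 / 4.98 | 4.92 / 4.94 |
| 25% | 4.94 / 5.00 | 4.88 / 4.94 | 4.79 / 4.85 |
| 100% | 4.75 / 5.00 | 4.53 / 4.77 | 4.15 / 4.38 |

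With everyone lost, cases missed are 0.9 at HR 2 and 1.6 at HR 4.

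Over q = 5 to 20%, HR = 1 to 5 and f = 0 to 100%, the nominal rate runs from 5.00% to 3.23% and Kaplan-Meier from 5.00% to 3.60%. Both low ends need q = 20%, HR = 5 and every progressor lost. With at most 25% lost, the worst nominal value is 4.56%, a shift of 0.44 points or 0.8 of a case.

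**The case against.** Much of the plan points towards continued observation. The sentence after the withdrawal rule in 4.4 keeps these subjects eligible for drug and scheduled visits. Subjects on drug are explicitly kept on schedule to Week 240, and 1.3.1 says the same for those off drug. Table 1 has ultrasound and AFP at every visit, including the withdrawal column. The protocol also expects many progressors to stay on drug: 5.1.2 lengthens the TDF dosing interval when creatinine clearance falls below 50 mL/min, 6.3.2 stops drug for renal reasons only at confirmed creatinine above 2.5 mg/dL, and 6.3.1.1 says treatment-free follow-up is to be avoided in bridging fibrosis or cirrhosis.

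This defeats two readings that a reader might infer. The first is that a non-HCC event ends observation for HCC. Section 4.4 taken whole contradicts itself; it is not a clear stop. The second is that the post-event assessment list in 3.1 drops ultrasound and AFP. That list directly follows a promise of the original schedule and also omits other Table 1 items such as FibroScan and serology. Nothing says it is exhaustive.

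It can also be said that the nominal rate is pulled down by any dropout, that 15% is already planned for, and that the Study Procedures Manual, which is not available here, may settle conduct. Those points limit the size. They do not remove the defect: three sections permit departure and one directs it, for subjects still at risk, and the rules for subjects off drug do not agree.

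**Conclusion.** The conflict is real and worth correcting, but it is a conflict and not a rule that stops HCC observation. The plan disagrees with itself on whether withdrawal after a non-HCC progression event is required, optional or compatible with full follow-up, and it does not guarantee HCC surveillance for subjects who leave or come off drug.

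The direction of bias in the nominal rate is certain if any HCC is missed; the amount is not. At 10% progression, a hazard ratio of 2 to 4 and 10 to 25% lost, all assumed, the nominal shift is about 0.05 to 0.2 points and the Kaplan-Meier shift about 0.02 to 0.15. Even the extreme corner of the assumed grid (1.8 points nominal, 1.4 Kaplan-Meier) lies inside the planned 3.4-point half-width. If no progressor is lost there is no bias, and if progression does not raise HCC risk the Kaplan-Meier estimate is unbiased. Site divergence is possible under this text but not shown. The case for acting is that the remedy is cheap and removes a one-directional error.

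**What to change.** In the protocol summary, Protocol 3.1, Protocol 4.4 and SAP 3.1, replace withdrawal at the primary endpoint with:

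*A non-HCC progression event does not end study follow-up; the subject may stop study drug, but the 12-weekly ultrasound and AFP in Table 1 continue to Week 240, on or off drug, unless consent is withdrawn.*

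State also that, for these subjects:
- the Table 1 footnote 3 evaluation is in addition to this schedule, not instead of it;
- a drug interruption of 28 days or more ends study drug, not HCC surveillance.

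Optionally, SAP 7.1 could count departures after a primary-endpoint event as a separate disposition line, since the listed reasons have none.

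The cost is wording in four places plus the two clarifications. Both tests are already scheduled. The burden is extra visits for off-drug progressors who would otherwise have left. At an assumed 5 to 20% progression there would be about 9 to 37 progressors in all (0.05 × 186 to 0.20 × 186), and only part of them would add visits.
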